The one-sided significance thresholds for the Lan-DeMets alpha spending function with an O'Brien-Fleming boundary will be recalculated at the time of each interim analysis based on the estimate of the information fraction. The estimate of the information fraction is a fraction in which the numerator is the sum of the time between the baseline WBCT assessments and the last timepoint for each subject for NHS and MOVE assessments; the denominator is the sum of the time between the baseline WBCT assessments and the expected last timepoint (at the time of the final analysis) for each subject for NHS and MOVE assessments.

At the final analysis, the information fractions at the previously conducted interim analyses will be re-calculated using the observed information, i.e., the sum of the time between the baseline WBCT assessments and the last timepoint for each subject for NHS and MOVE assessments. The critical p-value for the final analysis will be set such that the remaining alpha is spent. The information fraction at the final analysis will be set to 100%.

Study success was to be declared if the posterior probability that palovarotene reduces the change in new HO volume is greater than 1 minus the one-sided significance threshold. For

example, the posterior probability that palovarotene reduces the annualized change in new HO volume must be greater than 0.9810 to declare study success at the final analysis in the scenario above. Because the futility boundary was crossed at the second interim analysis, i.e., the posterior probability that $\gamma < 0.7$ (at least a 30% reduction in annualized new HO volume on the square-root scale) was less than 5%, all subsequent analyses of efficacy data will be supplied without applying thresholds for success or futility, as these thresholds are no longer relevant.

Sensitivity Analyses

The following sensitivity analyses will be conducted after the third interim analysis to examine the robustness of the Bayesian compound Poisson analysis without the square-root transformation, unless otherwise specified. All assessments on or before December 4, 2019, for subjects <14 years old on the date of their assessment and assessments on or before January 24, 2020, for all other subjects, will be used. Note that, given the consistency of results between the Bayesian compound Poisson and wLME analyses observed at the second and third interim analyses, the sensitivity analyses below will utilize both methodologies, as described. The results may be summarized jointly in forest plots, as appropriate.

To assess impact of differences between NHS and MOVE:

- Adjustment for additional baseline covariates: This sensitivity analysis will extend the primary efficacy analysis to include additional baseline covariates. These will include baseline HO volume divided by age, age, sex, months since last flare-up, and CAJIS. The palovarotene treatment effect will be estimated using the Bayesian compound Poisson distribution with all covariates included. A similar wLME will also be performed.
- Propensity score analysis: The propensity score, defined as the conditional probability of being treated given the baseline covariates, can be used to balance the baseline covariates across treatment groups.³ Therefore, it can reduce potential bias due to imbalances in the distributions of demographic and disease characteristics between the NHS and MOVE Trial. The propensity scores will be derived from a logistic regression model with the following covariates: baseline HO volume divided by age, age, sex, months since last flare-up, and CAJIS. Each subject's propensity score will be estimated from the logistic regression model, and subjects will be grouped by quartiles of their propensity scores. Propensity score quartile will be used as the only covariate in the Bayesian compound Poisson analysis. wLME will be conducted for each quartile and overall using the 5-level factor as a covariate (in addition to treatment).
- Restriction to subjects contributing follow-up for both the NHS and MOVE Trial: This analysis will use the wLME analysis method on the subset of the MOVE subjects who transitioned from the NHS and have annualized rates of new HO for both studies. Baseline HO volume divided by age will be the only covariate included in the model, in addition to the factor identifying the study of origin.
- As requested by regulatory agencies, a matched pairs analysis – including subjects who participated in either MOVE or NHS but not both studies – was performed. Caliper-matching used propensity scores described in this SAP. The analysis used a paired t-test.

To assess impact of differences in length of follow-up between NHS and MOVE:

- Analysis restricting subjects to specific durations of follow-up: The WBCT dataset will be restricted to observations associated up to 1-year – interpreted as assessments within the first 15 months of study participation (i.e., midway between Month 12 and Month 18 for MOVE) – and, separately, with up to 2-years of follow-up – interpreted as assessments within the first 27 months of study participation. The analysis method will be wLME.

To assess impact of missing data in MOVE:

- Missing data sensitivity analysis using a tipping point approach: Subjects who discontinue the MOVE study will have volume of new HO imputed using the wLME-modeled treatment effect. The multiple imputations will be scaled to induce 0%, 25%, 50%, 75%, and 100% reductions in the palovarotene treatment effect. The 0% corresponds to subjects who discontinue the MOVE Trial having the same distribution for number of body regions with new HO and change in HO volume per region as the MOVE subjects who did not discontinue; and 100% corresponds to subjects who discontinued the MOVE Trial having the same distributions as the NHS subjects. Missing data will be imputed for the visits in MOVE that were either missed or would have been missed due to study discontinuation prior to December 4, 2019 / January 24, 2020. Analyses in which subjects who discontinue the NHS have volume of new HO imputed may also be considered, while noting that the majority of subjects who discontinued NHS did so to enroll in an interventional study, e.g., MOVE or less frequently, Study PVO-1A-201.

To assess robustness of efficacy signal against choice of wLME as post-hoc analysis:

- Analysis using generalized estimating equations (GEE): A GEE model will be fit to the annualized change in new HO and the empirical variance estimator will be used for inference. Weights will be used to account for the different lengths of observed subject follow-up. Baseline HO volume divided by age will be included in the model as a covariate and a compound-symmetric working correlation matrix will be used. The GEE model takes a different approach to account for within-subject correlation compared to the primary analysis.

To assess consistency of efficacy signal across subgroups:

- Subgroup analyses: The subgroup analyses will also be performed for all efficacy endpoints to examine the consistency of the estimated treatment effect by sex (Male, Female), Asian ancestry (Yes, No), and age (≥ 12 , ≥ 14 , ≥ 18 , $\geq 12 - < 17$ years) and age by sex (< 8 years for Females or < 10 years for Males; ≥ 8 years for Females or ≥ 10 years for Males; $\geq 8 - < 14$ for Females or $\geq 10 - < 14$ years for Males).

The inferential analysis method used in the subgroup analyses will be Bayesian compound Poisson analysis and wLME for new HO volume by age and age by sex, and for wLME for all other endpoints and factors, with the exception of the above

contingency table analysis of proportions of subjects with new HO and flare-ups; this analysis will employ Fisher's exact test.

To assess impact of the difference in WBCT visit schedules between MOVE and NHS:

- The impact of the difference in WBCT visit schedules between MOVE and NHS is assessed by analyzing the data as if the WBCT assessments in MOVE were conducted annually rather than biannually. This is intended to investigate whether the differences in visit schedules introduced bias, with and without use of the square-root transformation. Estimates of γ , $\theta_{1,1}$, $\theta_{2,1}$ will be compared between Bayesian compound Poisson analyses, with and without square-root transformation, with the observed biannual MOVE WBCT and with the dataset collapsed to simulate annual MOVE WBCT assessments.

It must be noted, however, that this analysis does not eliminate the effect of the more frequent assessments in MOVE; as described in the MOVE and NHS Independent Review Charter, radiologists only measured the amount of HO if they first determined there was new HO relative to the previous timepoint. If there was no new HO, the volume from the previous assessment was carried forward. Because the read process for the 12-month timepoint used the 6-month assessment and the read process for the 24-month assessment used the 18-month assessment, this analysis can investigate only the bias introduced by the differences in visit schedules into the analysis, not the differences in visit schedules per se.

In any case, the sponsor believes that the differences in visit schedules could result in biases of the event rate treatment effect $\theta_{1,1}$ against palovarotene and growth rate treatment effect $\theta_{2,1}$ in favor of palovarotene but that, in the absence of the square-root transformation, these biases are offset, yielding an unbiased estimate of $\gamma = \theta_{1,1} * \theta_{2,1}$.

With the square-root transformation, however, the bias against palovarotene in the event rate treatment effect $\theta_{1,1}$ is unchanged, while the bias on growth rate treatment effect $\theta_{2,1}$ in favor of palovarotene is reduced, yielding a bias in γ against palovarotene.

Consider identical growth events in NHS and MOVE of 8000 mm³ that is split across two six-month intervals in the MOVE study as 4000 mm³ in the first 6-month interval and 4000 mm³ in the next 6-month interval. This registers as two events in one year on MOVE, but just one event in NHS. Similarly, the growth rate, conditional on there being an event, is 2X higher in NHS than MOVE, i.e., 8000/4000=2, in the absence of a square-root transformation. With a square-root transformation, however, the growth rate per event is only 1.4X higher in NHS than MOVE, i.e., $\sqrt{8000}/\sqrt{4000} \sim 1.41$.

A similar comparison of analyses will be performed with wLME, where negative values are zeroed out by region and then square-root transformed, because the bias illustrated above from the square-root transformation should also affect this annualized HO endpoint, which is constructed using new HO observed at each visit.

Analyses of Secondary Efficacy Endpoints

Proportion of Subjects with Any New HO (Key Secondary Endpoint) and Number of Body Regions with New HO

The proportion of subjects with any net new HO (at Month 12) – and number of body regions with any net new HO (at Month 12) – will be compared between the MOVE and NHS groups using the Bayesian compound Poisson model used in the primary efficacy analysis. (New HO is deemed to be present in a body region qualitatively if the volume of net new HO is greater than zero, i.e., the change in volume of HO in a region between two timepoints is positive when new HO is identified qualitatively) Gibbs sampling from the posterior distribution will be generated to compute the posterior distribution of $\theta_{1,1}$, the multiplicative effect of palovarotene treatment on the rate of body regions with new HO. Because, within the compound Poisson model, $\theta_{1,1} < 1$ implies both a lower proportion of subjects with any new HO and a smaller number of body regions with new HO for palovarotene-treated subjects, the inference is identical for these two secondary endpoints. The probability of this ratio being less than 1 must be greater than 0.975 to declare statistical significance.

Inference on $\theta_{1,1}$ from the sensitivity analysis analyzing the data as if the WBCT assessments in MOVE were conducted annually rather than biannually will also be relevant, given the concerns about bias in estimating $\theta_{1,1}$ even in the absence of square root transformation will be summarized.

Tables will be provided summarizing the number and percentage of subjects with any net new HO by study visit and overall. In these tables, Month 12 incidence will be compared using an exact test for the difference in proportions.

Tables will also be provided summarizing the number of body regions with new HO by study visit and overall. The body regions with new HO will also be summarized by study visit and overall. In these tables, Month 12 counts will be compared using a negative binomial regression.

Flare-up Rate Per Subject-Month Exposure

The flare-up rate per subject-month exposure will be compared using a negative binomial regression on the number of flare-ups. An offset variable equal to the log of the number of years of follow-up will be included to convert the estimate to annualized rate.

In the NHS study, events were considered flare-ups when two or more flare-up signs were reported. This is different from the MOVE study, which defines a flare-up as an event with one or more flare-up sign. The analysis of the proportion of subjects reporting flare-ups will restrict the MOVE flare-ups to those events that match the NHS study definition.

Descriptive tables will be provided summarizing the number of flare-ups and the rate of flare-ups by study visit, by age group and overall.

Proportion of Subjects Reporting Flare-ups

The proportion of subjects reporting flare-ups will be compared between untreated and treated subjects using an exact test for the difference in proportions.

As with flare-up rate analysis, this analysis will be performed restricting the MOVE flare-ups to those events that match the NHS study definition.

Descriptive tables will be provided summarizing the number and percentage of subjects with any flare-up by study visit, by age group, and overall.

Analyses of Exploratory Endpoints

The exploratory efficacy endpoints, including change from baseline in CAJIS Total score, CAJIS Upper Extremities subscore and CAJIS Mobility subscore; FOP-PFQ total score; and PROMIS Global Physical Health and Global Mental Health T-scores; will be summarized by visit using descriptive statistics for the Principal FAS and presented for the Supplementary FAS in listings.

Additional exploratory endpoints of incidence and volume of “catastrophic HO” will also be described and compared between MOVE and NHS for the Principal FAS. It has been observed – after unblinding at the second interim analysis – that a minority of subjects develop large amounts of HO in a year; the incidence of subjects with at least 50,000 mm³ and 30,000 mm³ of new HO across all body regions in each year of study will be summarized.

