#### Chronic Treatment: Part B

The assessments conducted in Part A will continue into Part B except that WBCT imaging will be performed annually thereafter at Months 36 and 48.

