The total blood volume drawn from a subject over the course of the entire study (48 months) will range from approximately 66 mL (in the case of no flare-ups) to 182 mL (in the case of two expected flare-ups treated per year, or a total of eight flare-ups treated during the entire study). In the event that the total drawn blood volume exceeds the limits established by the clinical site for pediatric subjects, then priority will be given to the key safety laboratory tests, as outlined in the clinical safety laboratory manual. This will ensure that the total blood volume drawn is within the established limits.

The Investigator will be provided all laboratory results and will review and assess out-of-range findings for clinical significance. Any post-baseline abnormal laboratory value assessed as clinically significant will be recorded as an AE. It is recognized that performing phlebotomy in subjects with FOP is very challenging due to their multiple ankyloses and the potential to cause injury resulting in a flare-up following multiple attempts. The Investigator will be notified about any protocol-specified safety laboratory test that could not be obtained despite at least two attempts. Should this occur, or for those samples that were drawn but were not usable (eg, quantity not sufficient, clotted, sample lost, etc.), the Investigator will assess the subject's condition and determine whether repeated attempts should be made to obtain the missing

laboratory data for that time point, or reassessed at the next scheduled time point based on the subject’s current clinical status (eg, AEs, vital signs) and previous laboratory measures.

Table 5 presents the clinical laboratory parameters that will be assessed in this study.

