2.3 Analysis Populations

The MOVE Trial subjects will be grouped into the following populations for analysis:

- The Principal Enrolled Population (Principal EP) includes all subjects with the R206H ACVR1 mutation who have not previously been treated with palovarotene and who sign the informed consent form and meet all eligibility criteria of the MOVE Trial. For the NHS, the Principal Enrolled Population will include all subjects enrolled.
- The Principal Full Analysis Set (Principal FAS) includes all enrolled subjects in the Principal EP who have a baseline HO volume measurement and at least one post-baseline HO volume measurement in the MOVE trial. For efficacy comparisons to the NHS, the Principal FAS will also include subjects enrolled in the NHS with available baseline and at least one post-baseline HO volume measurement.
- The Principal Per-Protocol Set (Principal PPS) is a subset of the Principal FAS including subjects with no major protocol deviations that are expected to interfere with assessments of the primary endpoint, and with at least 80% compliance to the study drug regimen. For efficacy comparisons to the NHS, the Principal PPS will also include subjects in the NHS with available baseline and at least one post-baseline HO volume measurement and with no major protocol deviation that are expected to interfere with assessments of the primary endpoint. Note that no analyses using the Principal PPS are planned after the interim CSR used to support the global regulatory filings.
- The Principal Safety Set (Principal SS) includes all enrolled subjects with the R206H ACVR1 mutation receiving at least one dose of palovarotene in the current study. For safety comparisons to the NHS, the Principal SS will also include subjects enrolled in the NHS with available post-baseline follow-up.
- The Principal Pharmacokinetic Set (Principal PS) includes all enrolled subjects with the R206H ACVR1 mutation receiving at least one dose of palovarotene and providing evaluable pharmacokinetic data in the current study.
- Principal Restart Full Analysis Set (Principal RFAS) includes all enrolled subjects in the Principal EP who restarted palovarotene therapy after January 2020 and have at least two assessments on or after restart e.g. 2 WBCT scans for HO volume measurements in the MOVE trial. Analyses involving this population will primarily be descriptive and will include records after palovarotene restart.

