2.4.4 Analyses of Efficacy Endpoints

The efficacy endpoints will be analyzed using the Principal FAS. Analyses using the Principal PPS will be performed as noted. Listings will be generated for the Supplementary FAS.

Note that no statistical inference is planned to be included in the descriptive analysis to be conducted before the first formal interim efficacy analysis; the inference described in this section will be conducted for the three interim efficacy analyses.

In order to address the prolonged interruptions in dosing in subjects <14 years old upon US FDA's institution of a partial clinical hold due to premature physéal closure (PPC) on December 4, 2019 and interruptions in dosing for the remaining subjects on January 24, 2020 due to the crossing of the futility boundary at the second interim analysis, analyses of all efficacy endpoints will include assessments collected on or before these interruptions, unless otherwise specified. (Assessments were to continue as planned during the interruptions.) For IA3, analyses in which all timepoints (available at IA3) are included, irrespective of dosing interruption, will also be conducted for the primary analysis (and additional analysis without the square-root transformation) and secondary analyses to aid in the interpretation of the efficacy results.

Note that, due to the prolonged interruption, IA3 provides the best description of efficacy of palovarotene and is determined to be the 'final analysis' for efficacy.

Additional analyses will be performed after database lock in which all WBCTs are included. E.g., an analysis comparing annualized new HO volume with NHS will be performed using GEE – Bayesian analyses are not planned. A separate analysis will also be performed for subjects who re-started palovarotene after the interruptions described above in the Principal RFAS. Baseline will be defined as the first WBCT scan obtained after re-start that was not obtained during a flare-up or within 1 month of the end of a flare-up.

The sponsor also notes that because the futility boundary was crossed at the second interim analysis, all subsequent analyses of efficacy data will be supplied without applying thresholds for success or futility, as these thresholds are no longer relevant.

Analyses of Primary Efficacy Endpoint

Primary Analysis

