Hearing was assessed via age-specific pure tone audiogram monitoring via baseline and follow-up age-specific hearing evaluation tests. A listing will summarize by-subject results.

Pregnancy and Teratogenicity Assessment

Pregnancy and pregnancy outcomes were monitored throughout the study. A listing will summarize by-subject results.

Bone Safety Assessments

Two events led to a prolonged treatment interruption period. The first interruption occurred following a partial clinical hold issued by the US Food and Drug Administration (FDA) on the 4 December 2019 for subjects under 14 years of age in palovarotene clinical studies due to the identification of the risk of PPC. The second interruption occurred following the outcome of the PVO-1A-301 second interim analysis that crossed the threshold for futility, which resulted in the per-protocol treatment discontinuation of subjects ≥ 14 years of age on 24 January 2020.

Bone safety data will be described for following time periods:

The Original Baseline Period

The original baseline period will be defined by the original baseline through February 2020.

The Interruption (Off-treatment) Period

The baseline for the off-treatment period is the earlier of the first assessment while off-treatment or the assessment within 1 month prior to the last dose of palovarotene. Bone growth assessments during the interruption period included subjects in the off-treatment population, which was defined as subjects < 18 years of age at first study entry who interrupted palovarotene after the clinical hold date and did not re-initiate treatment and who had an off-treatment baseline and post-off-treatment baseline visit.

The end of the interruption period occurred either at the end-of-treatment/end of study visit if the subject discontinued from the study, at the end-of-study visit if they completed the study, at the new baseline if the subject re-initiated palovarotene treatment.

The New Baseline Period

A new baseline was established by the re-initiation of palovarotene dosing following the interruption period. New baseline bone growth assessments includes all subjects who had a new baseline and a post-new baseline visit and received at least one dose of palovarotene after the new baseline visit date. The new baseline visit date was defined as the date of the last visit prior to the re-initiation of palovarotene treatment following the interruption period.

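### In the restart-population efficacy analysis, an on-drug flare-up close to a scan can postpone the baseline, so that some bone formed on drug counts as baseline bone

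*SAP*

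**What the plan says.** SAP 2.3 defines the Principal RFAS as Principal EP subjects "who restarted palovarotene therapy after January 2020 and have at least two assessments on or after restart", giving two WBCT scans as the example. It does not require those scans to be free of flare-ups. It adds: "Analyses involving this population will primarily be descriptive and will include records after palovarotene restart".

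SAP 2.4.4 sets the efficacy baseline: "Baseline will be defined as the first WBCT scan obtained after re-start that was not obtained during a flare-up". The same sentence goes on to rule out scans in the month after a flare-up ends, so that the baseline must be a scan "that was not obtained during a flare-up or within 1 month of the end of a flare-up". The date of onset of the flare-up plays no part.

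Other restart baselines differ. For bone safety, SAP 2.4.5 says: "The new baseline visit date was defined as the date of the last visit prior to the re-initiation of palovarotene treatment". For baseline characteristics of the RFAS, SAP 2.4.1 uses the first record after re-start.

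Scans are six-monthly to Month 24 (Protocol 7.4.1). In Part B, "WBCT imaging will be performed annually thereafter at Months 36 and 48", with a further scan at end of treatment or study.

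**The concern.** A baseline should be fixed by something settled before the period being measured. Here the baseline scan is always an on-drug scan, and which one is chosen depends on whether the subject flared on drug near a scheduled scan. Flare-ups are closely tied to new HO and trigger the higher-dose regimen, so the choice depends on something close to the outcome.

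There are two consequences. HO that formed on drug before the deferred scan is no longer counted as new. Frequent flarers also lose more follow-up than others, and some lose all of it. The RFAS analysis is the only efficacy analysis confined to treatment after re-start, so a reader of the final report will look to it for how patients fared on resumed drug.

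**Working it through.** The plan gives no sample size, flare-up rate or HO figure for the RFAS, so there is no stated result to reproduce. The size can only be illustrated.

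**1. What the rule does.** Take a subject who re-starts, flares on drug and is scanned during that flare-up or within a month of its end. That scan is passed over.
- If the next scan is the Month 24 scan, baseline moves by about 6 months.
- If the Month 36 scan is passed over, baseline becomes Month 48, and nothing follows unless there is a separate end-of-study scan.
- The subject still meets the two-assessment rule in SAP 2.3.

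Two limits apply. A flare-up that ended more than a month before the scan moves nothing. A flare-up after the baseline scan stays in the measured effect.

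**2. How often a candidate scan is skipped.** Let r be flare-ups per year, occurring as a Poisson process, and D their length in weeks. One month is 52/12 = 4.33 weeks.

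P(skipped) = 1 − exp[−r × (D + 4.33)/52]

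| r per year | D = 4 | D = 8 | D = 12 |
|---|---|---|---|
| 0.5 | 8% | 11% | 15% |
| 1 | 15% | 21% | 27% |
| 2 | 27% | 38% | 47% |

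For r = 2 and D = 12: 1 − exp(−2 × 16.33/52) = 1 − exp(−0.628) = 0.47. The rate of 2 comes from the upper end of a blood-volume range in Protocol 7.2.6 ("in the case of two expected flare-ups treated per year"), which is not an efficacy assumption. D is assumed; 12 weeks is the length of a treatment course, not of a flare-up.

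These figures count flare-ups of any onset. They are purely on-drug if the scan falls at least D + 4.33 weeks after re-start. For an earlier scan, the time since re-start replaces D + 4.33. At 2 months (8.67 weeks) with D = 12, the on-drug share is 1 − exp(−8.67/52) = 15% at one flare-up per year and 1 − exp(−2 × 8.67/52) = 28% at two.

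**3. What it does to the annualised rate.** A simulation of 20,000 subjects per scenario used these assumptions, none of them from the documents:
- one unit of HO per flare-up, accruing over 12 weeks;
- D of 4 or 12 weeks;
- a mean of 1 or 2 flare-ups per year, the same for every subject, or a mean of 2 varying between subjects (gamma, SD 2);
- the same rate before and after re-start;
- total HO divided by total follow-up.

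| Re-start and later scans | Flare-up rates | Annualised HO against truth | On-drug flare-ups starting before baseline | No scan after baseline |
|---|---|---|---|---|
| Month 16; scans 18, 24, 36, 48 | Equal | 4–5% low | 10–27% | 0.3–10% |
| Month 16; same scans | Varying | 18–32% low | 28–48% | 5–14% |
| Month 30; scans 36, 48 | Equal | 10–11% low | 43–65% | 15–47% |
| Month 30; same scans | Varying | 33–46% low | 63–75% | 25–38% |

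A baseline at the first post-restart scan with no flare-up exclusion absorbs 6% (Month 16) or 33% (Month 30) of on-drug flare-ups, yet returns the true annualised rate. A pre-restart baseline absorbs none and also returns it. So anchoring after re-start hides some HO without biasing the rate; in these scenarios the bias comes from the flare-up exclusion.

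**The case against.** The strongest reply is that a flare-free baseline is sensible. It avoids measuring from a scan taken while bone is forming, and it mirrors the enrolment criterion of no symptoms in the preceding 4 weeks. That stands as a reason to exclude flare-ups that began off drug. It does not extend to on-drug flare-ups, because the enrolment criterion acts before treatment.

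The endpoint is annualised, so deferring baseline removes follow-up time along with HO. A reader might infer a demonstrated bias in favour of palovarotene. The documents do not support that: the shortfall depends on the assumed accrual lag and, for the larger figures, on an assumed spread of flare-up rates.

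A reader might also infer that every flare-up after re-start shifts the baseline. Only one overlapping a candidate scan, or ending in the month before it, does so. Nor should the exclusion windows simply be added, as in 2 × (84 + 30)/365 = 62% of the year. That counts overlapping flare-ups twice; the Poisson figure for the same rate and length is about 47%.

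The contrast with bone safety has an explanation. Protocol 7.8 required radiographs within 12 weeks before re-start in skeletally immature subjects, but no whole-body CT. It listed CT among assessments that could be postponed and had it done once site visits resumed. SAP 2.4.4 says assessments were to continue during the interruption, but a pre-restart CT cannot be assumed for everyone. The different baselines are worth noting but do not prove an error.

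**Conclusion.** The point holds for the Principal RFAS efficacy analysis. Its baseline can be deferred by an on-drug flare-up, on-drug HO before the deferred scan is then not counted, and a subject can qualify for the population yet have nothing to analyse. That much follows from the wording alone.

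The size does not. The 15% to 47% of skipped scans assumes 1 to 2 Poisson flare-ups per year lasting 4 to 12 weeks. The likely direction is lower annualised new HO, through loss of frequent flarers and through accrual lag. Every simulated scenario pointed that way, but the range of 4% to 46% shows that the amount cannot be settled from the documents.

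It would be wrong to conclude that the trial's efficacy result is compromised. SAP 2.4.4 designates IA3 as the final efficacy analysis, applies no success or futility thresholds after the second interim analysis, and plans a GEE comparison with the natural history study using all WBCTs, in which HO after re-start is counted. The RFAS analysis is separate and mainly descriptive. The rule is worth correcting because the correction is cheap.

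**What to change.** 1. In SAP 2.4.4, apply the flare-up exclusion only to flare-ups with onset before re-start. On-drug flare-ups then no longer move the baseline. On-drug HO formed before the first post-restart scan is still absorbed, which is why item 2 is needed.
2. Add a sensitivity analysis with the last WBCT on or before re-start as baseline, where one exists, and show each subject's off-drug gap between that scan and re-start. Its drawback is that HO formed off drug in the gap is attributed to treatment. Dosing stopped around 24 January 2020 for subjects not already on hold and could resume only from 26 March 2020, site by site, and CT could be postponed, so the gap may not be short. For this reason it is better as a sensitivity analysis than as the main baseline.
3. Report how many subjects' baselines were deferred, by how long, and how many have no scan after baseline.
4. Amend SAP 2.3, which limits RFAS analyses to records after re-start, so that the sensitivity analysis may use an earlier scan.

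The cost is some SAP wording, one reprogrammed date, one extra run and a short listing. No new data are needed.
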